4.3.3.2 Imputation of Adverse Events in tabulations

- AEs with unknown intensity will be treated as “severe” for the tabulations.
- AEs with unknown relationship will be treated as “related” for the tabulations.
- AEs with unknown seriousness will be treated as “serious” for the tabulations.

There will be no imputation of AE data for the data listings. All data will be listed as recorded in Medidata Rave.

4.3.3.3 Imputation of PK elapsed times

PK analysis will, where data allow, be carried out using actual elapsed times determined from the PK sampling and dosing times recorded in the raw data. If actual elapsed times are missing, nominal times will be used.

4.3.3.4 Imputations of Laboratory Values

Values of the form “< x.x” (i.e., below the lower limit of quantification [LLoQ]) or “> x.x” (i.e., above the upper limit of quantification [ULoQ]) will be imputed as “x.x” in the calculation of summary statistics but displayed as “< x.x” or “> x.x” in the listings.

4.4 Software

All report outputs will be produced using SAS® version 9.4 in a secure and validated environment.

The PK parameters will be derived using non-compartmental methods in Phoenix® WinNonlin® Version 8.1 or higher (Certara).

4.5 Analysis Sets

4.5.1 Randomized set

The Randomized Set will consist of all participants randomized into the study.

4.5.2 Safety analysis set (SAF)

[figure not shown]
[figure not shown]
The safety analysis set will include all participants who were randomized and received any amount of IMP.

4.5.3 PK analysis set (PKS)

The PK analysis set will consist of all participants in the safety analysis set who received IMP and have evaluable serum PK data, with no important protocol deviations thought to impact on the analysis of the PK data.

Data from participants for whom the pre-dose concentration is > 5% of their respective Cmax for AZD8895 or AZD1061 may be excluded from the summary tables and figures and from the statistical analysis.

4.5.4 CCI

4.5.5 AZD8895 ADA Evaluable Analysis Set

The AZD8895 ADA Evaluable Analysis Set will include participants with at least 1 baseline and 1 post-baseline AZD8895 ADA measurement.

4.5.6 AZD1061 ADA Evaluable Analysis Set

The AZD1061 ADA Evaluable Analysis Set will include participants with at least 1 baseline and 1 post-baseline AZD1061 ADA measurement.

4.5.7 AZD7442 ADA Evaluable Analysis Set

The AZD7442 ADA Evaluable Analysis Set will include participants with either at least 1 baseline and 1 post-baseline AZD8895 or at least 1 baseline and 1 post-baseline AZD1061 ADA measurement.

4.5.8 Analysis sets summary

Upon database release, protocol deviation and the analyses population will be produced for review. An analysis set classification meeting will be arranged to discuss the outputs and to decide which participants and/or participant data will be excluded from certain analyses. Decisions made regarding the exclusion of participants and/or participant data from analyses will be documented and approved by the sponsor.

A summary on which analysis set will be used for each outcome variable is provided in Table 2.

Table 1 Summary of Outcome Variables and Analysis Sets

Outcome Variable	Analysis Set
PK Data	
PK concentrations	PKS
PK parameters	PKS
Study Population/Demography Data	
Disposition of participants	Randomized
Demography characteristics	SAF
Baseline and disease characteristics	SAF
Important protocol deviations	SAF
Medical history	SAF
Concomitant medications	SAF
Safety Data	
Exposure	SAF
AEs	SAF
Laboratory measurements	SAF

Outcome Variable	Analysis Set
Vital signs	SAF
ECGs	SAF
Injection site reaction	SAF
Anti-drug antibodies	
ADA assessments	AZD8895 ADA Evaluable Analysis Set; AZD1061 ADA Evaluable Analysis Set; AZD7442 ADA Evaluable Analysis Set
CCI [REDACTED]	
CCI [REDACTED]	CCI [REDACTED]

4.6 Study Participants

4.6.1 Disposition of Participants

A clear accounting of the disposition of all participants who enter the study will be provided, from screening to study completion.

Participant disposition will be listed and summarised for the Randomized Set.

A randomization listing will be presented and include the following: each participant's randomization number, the participant's full enrollment number, the treatment to which the participant has been randomized and the country where the study Clinical Unit is located.

Participants and/or data excluded from the PK analysis set will be listed including the reason for exclusion. Participant disposition will be summarized and will include the following information: number of participants randomized and dosed, number and percentage of participants completing the study and the number and percentage of participants who were withdrawn (including reasons for withdrawal).

Participant discontinuations will be listed including the date of study exit, duration of on-study follow-up, duration of safety follow-up and reason for discontinuation. A listing of informed consent response will also be presented.

4.6.2 Protocol Deviations

Important protocol deviations are defined as those deviations from the protocol likely to have an impact on the perceived efficacy and/or safety of study treatments. A full list of protocol deviations can be found in the study-specific Protocol Deviation Specification.

Deviations from the protocol will be assessed as “important” or “not-important” during a data review meeting prior to database lock. Important deviations from the protocol may lead to the exclusion of participants or data from the PKS. Deviations will be assessed before database lock.

Important deviations will include the following at a minimum:

- Violation of key inclusion and/or exclusion criteria
- Administration of prohibited concomitant medications that are expected to influence the measurement of the primary endpoint.
- Dosing deviations that are expected to influence the measurement of the primary endpoint.
- Time window deviations for safety and/or PK assessments
- Other procedural and study conduct deviations recorded by the study Clinical Unit on a protocol deviation log

All important protocol deviations will be listed.

4.7 Demographic and baseline characteristics

Demographic and baseline characteristics will be listed and summarised for all participants in the SAF by treatment group:

- Demographics (age [years], gender, race and ethnicity)
- Participant characteristics at baseline (height [cm], weight [kg], and body mass index [BMI] [kg/m^2])
- Stratification factors, as reported on the CRF (weight group and vaccination status)

The denominator for percentages will be the number of randomized participants.

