5.2. Procedures for Handling Incorrectly Randomized Participants

Participants who fail to meet the inclusion criteria or meet any exclusion criterion should not, under any circumstances, be randomized into the study. There can be no exceptions to this rule.

Where a participant, who does not meet the selection criteria, is randomized in error and this is identified before dosing, the participant should be withdrawn from the study. If a participant is withdrawn prior to dosing they will be replaced.

If a participant, who does not meet the selection criteria, has been dosed before the error is identified, the participant should be advised to continue follow-up visits and safety assessments to ensure their safety. The investigator will inform the AstraZeneca Lead Physician of the error immediately.

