11.1.2. Safety Analysis Set

The safety analysis set will include all participants who were randomized and received any amount of IMP.

Unless otherwise stated, the safety analysis set will be used for the presentation of all demographic and disposition data, safety analyses, as well as any immunogenicity assessments. Exposure to IMP will also be presented using the safety analysis set.

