11.2.3.1. Demographic and Baseline Data

Demographic variables (age, gender, race, ethnicity, height, weight, and BMI) will be listed by participant. Demographic characteristics (age, gender, race and ethnicity) and participant characteristics (height, weight, and BMI) will be summarized separately for all randomized participants by treatment group (Treatment Groups A, B, and C and Total). The denominator for percentages will be the number of randomized participants.

Medical history data will be listed by participant including visit, description of the disease/procedure, MedDRA SOC, MedDRA PT, start date and stop date (or ongoing if applicable).

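### SAP 4.7 counts baseline categories in the safety set but divides by the number randomised, so the percentages fall short of 100% if anyone is randomised and not dosed

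*SAP*

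**What the plan says.** SAP 4.7 names the table population: "Demographic and baseline characteristics will be listed and summarised for all participants in the SAF by treatment group". It lists age, gender, race and ethnicity; height, weight and BMI; and the stratification factors weight group and vaccination status. The analysis-set table in SAP 4.5.8 agrees on the population ("Demography characteristics SAF"). SAP 4.7 then ends with the denominator rule: "The denominator for percentages will be the number of randomized participants".

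The SAP defines the two sets separately:
- SAP 4.5.1: "The Randomized Set will consist of all participants randomized into the study".
- SAP 4.5.2: "The safety analysis set will include all participants who were randomized and received any amount of IMP".

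Three other places bear on the rule:
- SAP 4.2 gives a general rule that percentages use n as the denominator. In the same section, n for continuous data is the number of non-missing observations.
- Protocol 11.2.3.1 contains the same denominator sentence as SAP 4.7, but there the characteristics "will be summarized separately for all randomized participants by treatment group", so set and denominator match. Protocol 11.2.1 also names all randomised participants for these data.
- Protocol 11.1.2 says "the safety analysis set will be used for the presentation of all demographic and disposition data", but the sentence opens by limiting itself to cases where nothing else is stated.

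**The concern.** A percentage in a baseline table should be the share of the participants tabulated. Under SAP 4.7 the count comes from dosed participants and the divisor from everyone randomised. Any participant randomised and not dosed enters the divisor but can enter no category, so every share in that arm is too low and the categories do not add up to the whole.

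The rows affected are the categorical ones: gender, race, ethnicity, weight group and vaccination status. The last two are stratification factors. Vaccination status and body weight are also covariates in the primary model, so readers will look at these rows to judge balance between arms. If the number of undosed participants differs between arms, the shares shrink by different factors, and two arms with identical dosed populations would show different percentages.

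The programmer also has two denominator rules for one table, SAP 4.2 and SAP 4.7. The specific section would normally override the general one, so the mismatched rule is the one likely to be applied.

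**Working it through.** **Inputs**
- Planned size: 207 participants, 1:1:1, 69 per group (Protocol 3.1).
- Numerator set: dosed participants (SAP 4.7, 4.5.2 and 4.5.8).
- Denominator: randomised participants (SAP 4.7, 4.5.1).
- k, the number randomised but not dosed in a column: not given. Values of 0 to 5 are assumed for illustration.

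**Can k exceed 0?** Yes. Protocol 5.1 places randomisation on Day 1 before dosing. Protocol 4.3 covers participants randomised in error or withdrawn before dosing and makes replacement optional. Protocol 5.2 says "If a participant is withdrawn prior to dosing they will be replaced". Both cases, with and without replacement, are shown below.

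**Formula.** Let c be the count in a category among the dosed.
- Percentage as written: 100 × c / N_randomised.
- Percentage with matching sets: 100 × c / N_dosed.
- Ratio of the two: N_dosed / N_randomised.

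Summing over all categories (with missing values shown as a row) gives 100 × N_dosed / N_randomised. With replacement this is 100 × 69/(69+k) in an arm. Without replacement it is 100 × (69−k)/69. For the Total column, replace 69 by 207.

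The plan states no figure of its own on this point, so there is none to reproduce.

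**Sum of the category percentages as written**

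| k in the column | Arm, 69 dosed, k replaced | Arm, 69 randomised, no replacement | Total, 207 randomised, no replacement |
|---|---|---|---|
| 0 | 100.0% | 100.0% | 100.0% |
| 1 | 69/70 = 98.6% | 68/69 = 98.6% | 206/207 = 99.5% |
| 2 | 69/71 = 97.2% | 67/69 = 97.1% | 205/207 = 99.0% |
| 3 | 69/72 = 95.8% | 66/69 = 95.7% | 204/207 = 98.6% |
| 5 | 69/74 = 93.2% | 64/69 = 92.8% | 202/207 = 97.6% |

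**One row (assumed counts).** With 34 women among 68 dosed and 69 randomised, SAP 4.7 as written gives 34/69 = 49.3%. The share of the dosed is 34/68 = 50.0%. The shift is 0.7 percentage points.

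**Two arms (assumed counts).** Take a category that makes up half of the 69 dosed in each of two arms, with k=0 in one and k=3 in the other. The table would show 50.0% and 50.0% × 69/72 = 47.9%. That is a difference of 2.1 points that comes only from the denominator.

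**With matching sets.** Using the safety-set count for both, or the Randomized Set for both, returns the sum to 100% apart from rounding.

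**The case against.** The case for leaving the text alone has several parts.

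- **The effect may be nil.** Randomisation is on the dosing day, after eligibility is confirmed in the IRT, and Protocol 5.2 treats randomisation of an ineligible participant as something that must not happen. A reader might infer that the plan expects undosed participants. It only allows for them. This part stands: k is an assumption and may be 0.
- **A reader can recover the right share.** Counts are shown beside percentages, and SAP 4.6.1 reports the numbers randomised and dosed. That holds and limits the harm, but it does not make the rule correct.
- **The wording could be read leniently**, with the randomised participants taken to be those within the safety set. The SAP defines a separate Randomized Set, so the table should not depend on that reading.
- **The protocol is not at fault.** A reader might infer that Protocol 11.1.2 contradicts Protocol 11.2.3.1. It does not. Section 11.1.2 sets a default that yields where something else is stated, and 11.2.1 and 11.2.3.1 do state something else, consistently and with a matching denominator.
- **The tables without the two sites have no stated denominator.** SAP 4.14 adds demographic summaries that exclude sites #7808 and #7809 and leaves the details to the TFL shells, which are not among the documents. It is therefore an inference that the same mismatch would carry over. The corrected rule should be stated to cover those tables.

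**Conclusion.** The mismatch is real and lies within the SAP. Section 4.7 tabulates the safety set and divides by the number randomised, against the general rule in SAP 4.2. Followed as written, each categorical percentage in an arm is about 1.4% too low, relative to its correct value, for the first undosed participant (69/70 = 98.6%) and about 4.2% too low for three (69/72 = 95.8%). Both figures assume 69 dosed; the number undosed is not in the documents. With nobody undosed, the error is zero.

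The scope is narrow: categorical baseline rows only. Summaries of age, height, weight and BMI as continuous variables do not use this denominator. A reader might infer from the covariates in the primary model that the PK comparison is touched. It is not, because that model uses each participant's own data and none of these percentages. This is a minor reporting error.

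**What to change.** In SAP 4.7, use one set for both the counts and the denominator. Either choice is coherent:

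1. **Safety set for both.** Replace the denominator with the number of safety-set participants in the treatment group. This agrees with SAP 4.5.8 and needs one changed sentence.
2. **Randomized Set for both.** Keep the denominator and change the table population to all randomised participants. This agrees with Protocol 11.2.1 and 11.2.3.1. The baseline entries in SAP 4.5.8 must then change to match.

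With either choice, state that the rule in SAP 4.7 takes precedence over SAP 4.2 for these tables, show missing values as a row, and apply the rule to the demographic tables in SAP 4.14 that exclude the two sites.

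The cost is one or two sentences in the SAP, a table entry under option 2, and a check of the TFL shells. No protocol amendment and no new data are needed.

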4.8 Medical and surgical history

Disease related medical/surgical history will be coded using Medical Dictionary for Regulatory Activities (MedDRA). All disease related medical/surgical history (past and current) will be listed including visit, description of the disease/procedure, MedDRA SOC, MedDRA PT, start date and stop date (or ongoing if applicable) .

4.9 Prior and concomitant medications

Information on any treatment that the participant is receiving at the time of enrolment and all concomitant medications with reasons for the treatment, will be recorded in the Electronic Case Report Form (eCRF).

Prior and concomitant medications are defined based on start and stop dates as follows:

- Prior medications are those taken prior to study treatment with a stop date prior to first dose of study treatment.
- Concomitant medications are those with no stop date (ongoing) or a stop date on or after the first dose date of study treatment (and could have started prior to or during treatment).

Prior and concomitant medications will be listed for the SAF using the AstraZeneca March 2022 dictionary. They will be listed by participant and will include the following information: reported name, preferred term, the route of administration, dose, frequency, start date/time, duration, and indication.

The duration of the medication will be calculated as:

$$\text{Duration} = (\text{end date/time}) - (\text{start date/time}) + 1$$

The duration may be presented in hours or days in the listing depending on the applicability to the emerging data. For medications with partial or completely missing start date/times and/or end date/times, the duration will not be calculated.

Medications with missing or partial start date/time and/or end date/time such that it is not possible to classify as prior or concomitant will be considered as concomitant in the listings.

4.10 Pharmacokinetics

4.10.1 Analysis and Data Conventions

All summary tables and figures of PK concentrations and parameters, as well as all statistical analyses will be presented for the PKS, unless otherwise indicated. All PK listings and individual PK concentration versus time figures will be based on SAF, unless stated otherwise.

For PK parameters other than tmax and tlast, the following descriptive statistics will be presented: n, geometric mean (gmean), geometric standard deviation (gSD), geometric coefficient of variation (gCV), arithmetic mean, arithmetic standard deviation (SD), median, minimum, and maximum. For tmax and tlast, only n, median, minimum, and maximum will be presented.

The geometric mean will be calculated as e^μ where μ is the mean of the data on the logarithmic scale.

The geometric CV will be calculated as $100 \times \sqrt{\exp s^2 - 1}$ where s is the SD of the data on the logarithmic scale.

gmean \pm gSD will be derived as $\exp(\mu \pm s)$ where μ and s has been defined as above.

Individual concentrations below the Lower Limit of Quantification (LLOQ) of the bioanalytical assay will be reported as NQ (Not Quantifiable) in the listings with the LLOQ defined in the footnotes of the relevant TFLs. Individual plasma concentrations that are Not Reportable will be reported as NR and those that are missing will be reported as NS (No Sample) in the listings.

Plasma concentrations that are NQ, NR or NS will be handled as follows for the provision of descriptive statistics:

- Any values reported as NR or NS will be excluded from the summary tables and corresponding figures.
- At a time point where less than or equal to 50% of the concentration values are NQ, all NQ values will be set to the LLOQ, and all descriptive statistics will be calculated accordingly.
- At a time point where more than 50% (but not all) of the values are NQ, the gmean, gmean \pm gSD and gCV% will be set to NC. The maximum value will be reported from the individual data, and the minimum and median will be set to NQ.
- If all concentrations are NQ at a time point, no descriptive statistics will be calculated for that time point. The gmean, minimum, median and maximum will be reported as NQ and the gCV% and gmean \pm gSD as NC.
- The number of values below LLOQ ($n < \text{LLOQ}$) will be reported for each time point together with the total number of collected values (n).

Three observations $>$ LLOQ are required as a minimum for a plasma concentration or PK parameter (e.g. Cmax, Cmin, Clast) to be summarized. Two observations $>$ LLOQ are presented as minimum and maximum with the other summary statistics as NC.

If data are available for less than three participants, no summary statistics other than minimum, maximum and n will be presented.

4.10.2 Serum Concentrations

For the individual mAbs AZD8895 and AZD1061, as well as for the sum of the individual mAbs of AZD7442 (AZD8895 + AZD1061), the serum concentrations for each scheduled time point will be summarized by treatment group, treatment group and injection site, treatment group and bodyweight category, and treatment group, injection site, and bodyweight category using appropriate descriptive statistics, based on the PKS. A listing of all concentration-time data, ie, PK scheduled times, actual sample collection times, sample actual relative times, as well as derived sampling time deviations will be presented by treatment group (with injection site, and bodyweight category listed) for all participants in the SAF.

For AZD7442 concentration derived as the sum of AZD8895 and AZD1061 concentrations, the following cases of <LLOQ hold:

AZD1061 concentration	AZD8895 concentration	Result of AZD7442 concentration
<LLOQ	<LLOQ	<LLOQ
<LLOQ	XX	XX
YY	<LLOQ	YY
YY	XX	YY+XX
Missing	XX	Missing
YY	Missing	Missing
Missing	Missing	Missing

4.10.3 Pharmacokinetic Parameters

All PK parameters for the individual mAbs AZD8895 and AZD1061, as well as for the sum of the individual mAbs of AZD7442 (AZD8895 + AZD1061) will be summarized by treatment group, treatment group and injection site, treatment group and bodyweight category, and treatment group, injection site, and bodyweight category using appropriate descriptive statistics, based on the PKS.

All reportable PK parameters for the individual mAbs AZD8895 and AZD1061, as well as for the sum of the individual mAbs of AZD7442 (AZD8895 + AZD1061), including individual diagnostic and λ_z -related parameters, will be listed for each participant by treatment group (with injection site, and bodyweight category listed) based on the SAF.

Table 3 PK Parameters

Parameter	Definition
AUCinf	Area under serum concentration-time curve from time zero to infinity (final analysis only)
AUClast	Area under the serum concentration-time curve from time zero to time of last quantifiable concentration
AUC0-31d	Area under the serum concentration-time curve from time zero to 30 days post-dose
AUC0-61d	Area under the serum concentration-time curve from time zero to 60 days post-dose
AUC0-91d	Area under the serum concentration-time curve from time zero to 90 days post-dose
AUC0-181d	Area under the serum concentration-time curve from time zero to 180 days post-dose
Cmax	Maximum observed serum concentration
tmax	Time to reach maximum observed serum concentration
t½ λz	Half-life associated with terminal slope (λz) of a semi-logarithmic concentration-time curve (final analysis only)
tlast	Time of last quantifiable serum concentration
CL/F	Apparent total body clearance of drug from serum after extravascular administration (final analysis only)
Vz/F	Volume of distribution (apparent) based on terminal phase after extravascular administration (final analysis only)

The following diagnostic parameters will be provided as appropriate for the final analysis:

Parameter	Definition
λz	Apparent terminal elimination rate constant
λz lower	Lower (earlier) t used for λz determination

Parameter	Definition
λz upper	Upper (later) t used for λz determination
λzN	Number of data points used for λz determination
λz span ratio	Time period over which λz was determined as ratio of $t^1/\lambda z$
Rsq adj	Statistical measure of fit for the regression used for λz determination adjusted for the number of used data points (n obs)
AUCextr	Extrapolated area under the curve from tlast to infinity, expressed as percentage of AUCinf

